9.1.1.4 Preexisting Medical Conditions (Baseline Signs and Symptoms)

A preexisting medical condition should be recorded as an AE or SAE only if the frequency, severity, or character of the condition worsens during the study. When recording such events on an Adverse Event CRF, it is important to convey the concept that the preexisting condition has changed by including applicable descriptors (e.g., “more frequent headaches”).

9.1.2 Grading and Relationship to Drug

The descriptions and grading scales found in the CTEP Version 4 of the NCI Common Terminology Criteria for Adverse Events (CTCAE) will be utilized for AE reporting. CTEP Version 4 of the CTCAE is identified and located at: http://ctep.cancer.gov/protocolDevelopment/electronic_applications/ctc.htm. AEs not covered by specific criteria should be reported with common medical terminology and graded according to definitions provided in the CTCAE Version 4.

The relationship of event to study drug will be documented by the Investigator as follows:

- **Unrelated:** The event is clearly related to other factors such as the patient’s clinical state, other therapeutic interventions or concomitant drugs administered to the patient.
- **Unlikely:** The event is doubtfully related to investigational agent(s). The event was most likely related to other factors such as the patient’s clinical state, other therapeutic interventions, or concomitant drugs.
- **Possible:** The event follows a reasonable temporal sequence from the time of drug administration, but could have been produced by other factors such as the patient’s clinical state, other therapeutic interventions or concomitant drugs.
- **Probable:** The event follows a reasonable temporal sequence from the time of drug administration, and follows a known response pattern to the study drug. The event cannot be reasonably explained by other factors such as the patient’s clinical state, therapeutic interventions or concomitant drugs.
- **Definite:** The event follows a reasonable temporal sequence from the time of drug administration, follows a known response pattern to the study drug, cannot be reasonably

explained by other factors such as the patient's condition, therapeutic interventions or concomitant drugs; AND occurs immediately following study drug administration, improves upon stopping the drug, or reappears on re-exposure.

9.1.3 Reporting Adverse Events

Table 7. Guidelines for Routine Adverse Event Reporting for Phase I Studies (Regardless of Expectedness)

Attribution	Grade 1	Grade 2	Grade 3	Grade 4
Unrelated	X	X	X	X
Unlikely	X	X	X	X
Possible	X	X	X	X
Probable	X	X	X	X
Definite	X	X	X	X

Table 8. Guidelines for Routine Adverse Event Reporting for Phase IIb Studies (Regardless of Expectedness)

Attribution	Grade 1	Grade 2	Grade 3	Grade 4
Unrelated			X	X
Unlikely			X	X
Possible	X	X	X	X
Probable	X	X	X	X
Definite	X	X	X	X

All new routine AEs occurring between the start date of intervention until 30 days after the last intervention or until the event has resolved, stabilized, death, or a new treatment is started, whichever comes first, will be reported.

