1.6.2.4 INCB024360 Clinical Studies

INCB24360-101 has been evaluated in Phase I study conducted by Incyte Corporation in subjects with refractory solid tumors. The study has used a 3+3 dose escalation design, with doses of INCB024360 ranging from 50 mg once daily (QD) to 700 mg twice daily (BID). Three subjects have initiated treatment at 50 mg QD, 4 subjects at 50 mg BID, 3 subjects at 100 mg BID, 6 subjects at 300 mg BID, 11 subjects at 400 mg BID, 5 subjects at 500 mg BID and 4 subjects at 700 mg BID.

INCB024360 has generally been well tolerated. The most common Grade 1 or Grade 2 AEs in $\geq 20\%$ reported have been fatigue, nausea, decreased appetite, vomiting, constipation, abdominal pain, diarrhea, dyspnea, back pain, and cough. The most common Grade 3 or Grade 4 AEs were

abdominal pain, hypokalemia, and fatigue (9.6% each). Despite 1 patient reporting a dose-limiting toxicity (DLT) of radiation pneumonitis at 300 mg BID, additional subjects were enrolled at this dose and no additional DLTs were reported. At 400 mg BID, 1 patient reported a DLT of Grade 3 fatigue, with no additional DLTs at this dose level. Another patient at 400 mg BID developed asymptomatic and transient hypopituitarism after 1 cycle of therapy and was able to continue dosing with INCB024360. Among the 18 subjects treated at either 600 mg or 700 mg BID, no DLTs were observed. Dose escalation was completed based on preliminary pharmacokinetic and pharmacodynamic data, which demonstrated that doses of INCB024360 above 300 mg BID achieved exposures exceeding the IC90 determined in nonclinical models and, in pharmacodynamic assays, reached a plateau for Kyn/Trp levels and ratios. In the final cohort of 600 mg BID, the effect of food on INCB024360 absorption was evaluated. No objective responses were reported. At 2 months, stable disease was seen in 15 patients and lasted \geq 4 months in 7 patients. The main AE reported in subjects receiving more than 2 cycles of INCB024360 has been Grade 1 or Grade 2 fatigue.

In a combination study conducted by Incyte Corporation of INCB024360 and ipilimumab in metastatic melanoma patients, 5 of 7 subjects enrolled at a dose of 300 mg BID of INCB024360 plus 3 mg/kg of ipilimumab, developed Grade 3 or Grade 4 AST and ALT elevations between 2 and 4 cycles of treatment. Only one of these subjects had a bilirubin elevation of Grade 1.

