3 METHODOLOGY

3.1 Study Design

This is an open-label, Phase I/IIb study of the IDO inhibitor, INCB024360, in combination with DEC205mAb-NY-ESO-1 fusion protein (CDX-1401) given with adjuvant poly-ICLC in patients with NY-ESO-1 or LAGE-1 expressing epithelial ovarian, fallopian tube, or primary peritoneal cancer who are in remission.

For the Phase I component of the study, eligible patients will receive a fixed intracutaneous dose of DEC205mAb-NY-ESO-1 fusion protein (CDX-1401) (Day 1) given with subcutaneous adjuvant poly-ICLC (Day 1 and Day 2) for each 28 day cycle for a total of 5 cycles; and Cohort 1 patient enrollment will begin INCB024360 at a fixed daily dose of 300 mg BID orally (Cohort 1) for a total of 7 cycles. Based on the decision rules for DLTs, patients may be enrolled into Cohort -1. Cohort -1 will receive DEC205mAb-NY-ESO-1 fusion protein (CDX-1401) (Day 1) given with adjuvant poly-ICLC (Day 1 and Day 2) for each 28 day cycle for a total of 5 cycles, and daily oral INCB024360 100 mg BID (Cohort -1) starting on Day 1 for 7 cycles. Based on the decision rules for DLTs, patients may be enrolled into Cohort -2. Cohort -2 will receive DEC205mAb-NY-ESO-1 fusion protein (CDX-1401) (Day 1) given with adjuvant poly-ICLC (Day 1 and Day 2) for each 28 day cycle for a total of 5 cycles, and daily oral INCB024360 50 mg BID (Cohort -1) starting on Day 1 for 7 cycles.

After completing 1 cycle of treatment in the last patient from Cohort 1 (or Cohort -1 or Cohort -2), accrual into the randomized Phase IIb study (Cohort 2) will begin at the dose of INCB024360 that is determined to be safe in the Phase I trial (300 mg BID versus 100 mg BID versus 50 mg BID) in combination with CDX-1401. This is a randomized parallel design employing randomization for each patient enrolled to 1 of 2 groups (**Table 1**). Treatment cohorts include (i) DEC205mAb-NY-ESO-1 fusion protein (CDX-1401) given with adjuvant poly-ICLC alone and (ii) INCB024360 plus DEC205mAb-NY-ESO-1 fusion protein (CDX-1401) given with adjuvant poly-ICLC.

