9.1.1.3 Abnormal Laboratory Values

Only clinically significant laboratory abnormalities that require active management will be recorded as AEs or SAEs on the CRF (e.g., abnormalities that require study drug dose modification, discontinuation of study treatment, more frequent follow-up assessments, further diagnostic investigation, etc.).

If the clinically significant laboratory abnormality is a sign of a disease or syndrome (e.g., alkaline phosphatase and bilirubin 5 x the upper limit of normal associated with cholecystitis), only the diagnosis (e.g., cholecystitis) needs to be recorded on the Adverse Event CRF.

If the clinically significant laboratory abnormality is not a sign of a disease or syndrome, the abnormality itself should be recorded as an AE or SAE on the CRF. If the laboratory abnormality can be characterized by a precise clinical term, the clinical term should be recorded as the AE or SAE. For example, an elevated serum potassium level of 7 mEq/L should be recorded as “hyperkalemia”

Observations of the same clinically significant laboratory abnormality from visit to visit should not be repeatedly recorded as AEs or SAEs on the CRF, unless their severity, seriousness, or etiology changes.

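### Phase IIb reports Grade 1–2 adverse events only when the unblinded investigator judges them at least possibly related, so low-grade rates by arm may reflect attribution as well as drug effect

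*Combined protocol and SAP*

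**What the plan says.** Section 9.1.3 gives Table 7, "Guidelines for Routine Adverse Event Reporting for Phase I Studies (Regardless of Expectedness"), with all five attribution categories marked at all four grades. Table 8, "Guidelines for Routine Adverse Event Reporting for Phase IIb Studies (Regardless of Expectedness"), marks Grades 3 and 4 for every attribution, but marks Grades 1 and 2 only for Possible, Probable and Definite. The sentence under Table 8 sets the time window and does not restore the omitted cells.

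Section 9.1.2 says who decides: "The relationship of event to study drug will be documented by the Investigator as follows". The threshold that opens the low-grade cells is Possible: "The event follows a reasonable temporal sequence from the time of drug administration, but could have been produced by other factors". Probable and Definite also require that the event "follows a known response pattern to the study drug".

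Section 3.1 opens: "This is an open-label, Phase I/IIb study of the IDO inhibitor, INCB024360". No blinded or central attribution is described. Table 1 gives both randomised arms the same vaccine and poly-ICLC for 5 cycles; only Cohort 2b takes INCB024360, twice daily for 7 cycles.

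Section 9.1.1 defines an adverse event regardless of causality. Section 11.3 estimates a toxicity rate with a one-sided 95% Clopper-Pearson lower limit and does not restrict it to related events.

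**The concern.** Phase IIb is the only randomised comparison of the combination with the vaccine alone. For Grade 1–2 events, entry into the reported data depends on a judgement made by someone who knows whether the patient takes INCB024360. If that judgement leans on what is known about each product, the same mild complaint can be called Possible and reported in one arm, and called Unlikely and left out in the other.

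The protocol's own product information gives room for this. Section 1.6.2.4 lists the common low-grade events of INCB024360, and Section 1.6.1.2 lists the treatment-related events of CDX-1401 with adjuvant. Seven are on the first list and not on the second: diarrhea, constipation, vomiting, abdominal pain, back pain, cough and dyspnea. For these an investigator has a ready explanation in Cohort 2b and none in Cohort 2a.

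At stake is the descriptive low-grade tolerability profile by arm, the Section 11.3 rates where they include low-grade events, and what the Data Safety Monitoring Committee sees at its annual review (Sections 10 and 11.5).

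**Working it through.** **Is the restriction real?** Tables 7 and 8 stand side by side in Section 9.1.3. Table 7 is complete, so the four blank cells in Table 8 read as a deliberate Phase IIb rule and not as a lost part of the table. No other section asks for unrelated or unlikely Grade 1–2 events in Phase IIb.

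**Inputs.** From the documents: n = 25 per arm (Section 11.1) and the one-sided 95% Clopper-Pearson lower limit (Section 11.3). Assumed, because the documents give neither: the true Grade 1–2 rate p, taken equal in both arms, and the probability a that an event is judged at least Possible in each arm. The plan states no figure on this point, so there is none to reproduce.

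**Formula.** Expected reported count = n × p × a. Spurious difference in rates = p × (a for INCB024360 − a for control), which is zero when attribution is equal.

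**Worked case.** With p = 0.40, INCB024360 gives 25 × 0.40 × 0.8 = 8 and control gives 25 × 0.40 × 0.4 = 4. Full reporting gives 25 × 0.40 = 10 in each arm. The reported risk ratio is 8/4 = 2.0 with no true difference; the rate difference is 0.40 × 0.4 = 16 points.

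**Range of expected reported counts (INCB024360 vs control, of 25).**

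| True rate, both arms | Attribution 0.8 / 0.8 | 0.8 / 0.6 | 0.8 / 0.4 |
|---|---|---|---|
| 20% | 4 vs 4 | 4 vs 3 | 4 vs 2 |
| 40% | 8 vs 8 | 8 vs 6 | 8 vs 4 |
| 60% | 12 vs 12 | 12 vs 9 | 12 vs 6 |

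**What a reader of the safety table would see** (exact binomial sums, p = 0.40). With attribution 0.8 / 0.4, the INCB024360 arm shows the higher count with probability 0.88, against 0.44 when attribution is 0.8 in both arms. An unplanned two-sided Fisher test would give p ≤ 0.05 with probability 0.16, against 0.02.

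**Effect on the Section 11.3 limit.** The lower limit is 23.6% for 10/25, 17.0% for 8/25 and 5.7% for 4/25. Even with equal attribution of 0.8, the estimated low-grade rate is understated in both arms (8/25 instead of 10/25), although no difference between arms is created.

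**The case against.** The other side has a good deal in its favour, and most of it limits the point.

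- **Fatigue.** Section 1.6.2.4 says "The main AE reported in subjects receiving more than 2 cycles of INCB024360 has been Grade 1 or Grade 2 fatigue", and a reader might infer that this is the event most exposed. It is a weak example. Section 1.6.1.2 reports fatigue in 24% of patients given CDX-1401 with adjuvant, together with decreased appetite and nausea. Control-arm fatigue therefore fits a known vaccine pattern and may well be reported.
- **Cycles 6 and 7.** A reader might infer that control events are lost there because nothing is being given. Attribution is not the reason. The last control-arm study drug is poly-ICLC on Cycle 5 Day 2, which is Day 4 × 28 + 2 = 114. The 30-day window closes about Day 144, and Cycle 6 starts on Day 5 × 28 + 1 = 141. Most such events fall outside the window whatever Table 8 says, and changing Table 8 would not alter that.
- **Laboratory values.** Section 9.1.1.3 says "Only clinically significant laboratory abnormalities that require active management will be recorded as AEs or SAEs on the CRF", with dose modification among its examples. A reader might infer a second filter that works on one arm only. The other examples (stopping treatment, closer follow-up, further investigation) are open to both arms, and Section 6.3 lets the next-day poly-ICLC be omitted. Section 11.5 separately plans review and analysis of laboratory changes.
- **Lost data.** Table 8 governs reporting. Section 7.3 has adverse events assessed at each clinical visit in both arms, and the documents do not say what source records hold for unreported events. That they could never be recovered is not shown.
- **Scope.** Safety is a primary objective of Phase I, where Table 7 applies. In Phase IIb, Grade 3–4 events are reported at every attribution and all SAEs whether or not related (Section 9.2.2).
- **Low threshold.** Possible is easily met, and control patients also receive investigational agents, so control events can be missed but are not systematically excluded.

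What survives is that low-grade events pass through an unblinded attribution filter which nothing else in the plan removes.

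**Conclusion.** The point holds in a limited form. Phase IIb reporting of Grade 1–2 events depends on unblinded attribution, and attribution may differ by arm, most plausibly for events on the INCB024360 list and not on the vaccine list. Reported low-grade rates by arm may therefore reflect attribution as well as drug effect.

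The documents do not show that attribution does differ, and they give no attribution rates. The doubling in the worked case rests entirely on assumed values, and with equal attribution the spurious difference is zero. Nothing here touches the PFS analysis. This is an inexpensive improvement to the safety description, not a defect in the primary comparison.

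**What to change.** For Phase IIb, replace the Table 8 grid by the Table 7 grid: all grades and all attributions, in both arms. Keep attribution as a recorded field. Add to Section 11.3 that adverse events are summarised by arm regardless of cause, with related events as a secondary display. With an equal true rate, the expected counts are then equal whatever the investigator's view (10 against 10 in the example).

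Optionally, grade the hematology and chemistry results already scheduled in Table 3 directly from the laboratory data in both arms.

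The cost is one table, a sentence or two of text, and some extra adverse event entry for about 50 patients. No visit, test or treatment rule changes. If any Phase IIb patients have already been reported under Table 8, complete their low-grade events from source records where these allow, and state in the report which patients were collected under which grid.

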9.2 Serious Adverse Events

9.2.1 Definition

A serious adverse event (SAE) is any adverse event (experience) that in the opinion of either the investigator or sponsor results in **ANY** of the following:

- Death.
- A life-threatening adverse event (experience). Any AE that places a patient in the view of the Investigator or sponsor, at immediate risk of death from the reaction as it occurred. It does **NOT** include an AE that, had it occurred in a more severe form, might have caused death.
- Inpatient hospitalization or prolongation of existing hospitalization (for > 24 hours).
- A persistent or significant incapacity or substantial disruption of the ability to conduct normal life functions.

- A congenital anomaly or birth defect.
- Important Medical Event (IME) that, based upon medical judgment, may jeopardize the patient and may require medical or surgical intervention to prevent one of the outcomes listed above.

9.2.2 Reporting Serious Adverse Events

All new SAEs occurring from the start of treatment until 30 days after the last intervention or a new treatment is started, whichever comes first, will be reported. SAE's occurring after this time that the investigator determines to be possibly, probably or definitely related to the study intervention, should be reported.

The Roswell Park SAE Source Form is to be completed with all available information, including a brief narrative describing the SAE and any other relevant information. The site Investigator or designated research personnel will report all SAEs, whether related or unrelated, to the investigational agent(s) to the IRB in accordance with their local institutional guidelines.

INCB024360 Cohorts:

Investigators MUST report (within 1 business day), upon becoming aware, to Incyte, Sentrx, and Celldex ANY SAEs, whether or not they are considered related to the investigational agent(s)/intervention.

Incyte Pharmacovigilance
[name]
[name]
[contact]

All SAE reports are to be sent via e-mail to: [contact]

Sentrx
[name]
[name]
[name]
SAE Facsimile Number: Sentrx: [contact]
Sentrx Helpdesk Phone (Helpdesk support available 8am – 8 pm EST):
[contact] (toll free in US)
[contact] Ext: 250

Celldex Therapeutics, Inc.
SAE Reporting
[contact]
Email: [contact]

Exploratory Cohort with sirolimus (Roswell Park site ONLY):

Similarly as above, investigators MUST report (within 1 business day), upon becoming aware, to Sentrx, and Celldex ANY SAEs, whether or not they are considered related to the investigational agent(s)/intervention.

SAE's identified as an Unanticipated Problem by the Investigator must be reported. Please refer to **Section 9.3** for details on reporting Unanticipated Problems.

9.2.3 Follow-Up for Serious Adverse Events

All related SAEs will be followed to their resolution, until the study participant is lost to follow-up, the start of new treatment, or until the study investigator assesses the event(s) as stable or irreversible. New information will be reported when it is received.

9.3 Unanticipated Problems

9.3.1 Definition

An Unanticipated Problem (UP) is any incident, experience, or outcome that meets all of the following criteria:

- Unexpected (in terms of nature, severity, or frequency) given:
 - a) The research procedures that are described in the study-related documents, including study deviations, as well as issues related to compromise of patient privacy or confidentiality of data.
 - b) The characteristics of the patient population being studied.
- Related or possibly related to participation in the research (possibly related means there is a reasonable possibility that the incident, experience, or outcome may have been caused by the procedures involved in the research).
- Suggests that the research places patients or others at a greater risk of harm (including physical, psychological, economic, or social harm) than was previously known or recognized and if in relation to an AE is also deemed **Serious** per **Section 9.2**.

9.3.2 Reporting Unanticipated Problems

The Reportable New Information (RNI) Form will be submitted to CRS Quality Assurance Office within 1 business day of becoming aware of the Unanticipated Problem. After review, CRS Quality Assurance will submit the RNI to the IRB.

When becoming aware of new information about the Unanticipated Problem, submit the updated information to CRS Quality Assurance with an updated Reportable New Information Form. The site Investigator or designated research personnel will report all unanticipated problems, whether

related or unrelated to the investigational agent(s) to the **IRB in accordance with their local institutional guidelines.**

9.3.3 Notifying the Study Drug Provider

INCB024360 cohorts:

Expedited reporting by investigator to Celldex, Incyte, and Sentrx. Contact information can be found in section 9.2.2.

The investigator must inform Celldex, Incyte, and Sentrx in writing using an SAE form or MEDWATCH 3500A form of any SAE within 24 hours of being aware of the event. The written report must be completed and supplied by facsimile within 24 hours/1 business day. The initial report must be as complete as possible, including an assessment of the causal relationship between the event and the investigational product(s), if available. Information not available at the time of the initial report (e.g., an end date for the adverse event or laboratory values received after the report) must be documented on a follow-up report. An SAE is considered to be any adverse event that is life-threatening or that results in any of the following outcomes: death; inpatient hospitalization or prolongation of existing hospitalization; persistent or significant disability or incapacity; or a congenital anomaly or birth defect. Completed SAE reports are to be submitted to:

Celldex Therapeutics, Inc.
SAE Reporting
[contact]
Email: [contact]

Exploratory Cohort with Sirolimus:

Similarly as above, expedited reporting by investigator to Celldex and Sentryx.

9.4 FDA Reporting

When Roswell Park is the IND holder the following describes the FDA reporting requirements by timeline for AEs and new safety findings that meet the criteria outlined below:

Within 7 Calendar Days

Any adverse event that meets **ALL** the following criteria:

- Related or possibly related to the use of the study drug;
- Unexpected; and
- Fatal or life-threatening.

Within 15 Calendar Days

Any adverse event that meets **ALL** the following criteria:

- Related or possibly related to the use of the study drug;
- Unexpected; and
- Serious but not fatal or life-threatening.

Or meets **ANY** of the following criteria:

- A previous adverse event that is not initially deemed reportable but is later found to fit the criteria for reporting (report within 15 days from when event was deemed reportable).
- Any findings from other studies, including epidemiological studies, pooled analysis of multiple studies, or other clinical studies conducted with the study drug that suggest a significant risk in humans exposed to the drug.
- Any findings from animal or in vitro testing that suggest a significant risk for human patients including reports of mutagenicity, teratogenicity, or carcinogenicity or reports of significant organ toxicity at or near the expected human exposure.
- Any clinically important increase in the rate of occurrence of a serious, related or possibly related adverse event over that listed in the protocol or investigator brochure.

Sponsors are also required to identify in IND safety reports, all previous reports concerning similar adverse events and to analyze the significance of the current event in the light of the previous reports.

Reporting Process

The principal investigator or designee will complete and submit a FDA Form 3500A Medwatch for any event that meets the above criteria. Forms will be submitted to the CRS Quality Assurance Office via email to [contact].

